6.1.6 Body Surface Area (BSA) calculation and dose adjustments

BSA should be calculated according to local site standards. If none exists, the widely-used formula of Du Bois and Du Bois is suggested:

$$BSA = 0.007184 \times W^{0.425} \times H^{0.725}$$

Calculation of the BSA should be performed with a height and weight obtained within the past 24 hours prior to the start of chemotherapy, but need not be recalculated continuously for agents given by continuous infusion, unless weight has changed more than 10%. In the case of re-induction treatment, a new calculation should be made.

Doses of chemotherapy agents may be rounded +/- 5%, or less as defined by institutional policy, in order to accommodate standard vial sizes and reduce waste.

- 6.1.7 No lumbar punctures are mandated, and institutional practices and standards of care should be followed. Intrathecal chemotherapy given prophylactically should be given after platelet recovery from induction therapy. Intrathecal chemotherapy given for documented CNS disease may be given at any time at treating physician discretion.
- 6.1.8 If, during the pinometostat run-in phase (days 1-7) the disease is uncontrollable (either in terms of proliferation, or life-threatening organ dysfunction resulting from disease burden) with hydroxyurea in addition to the study agent, 7+3 induction therapy may be started early, if in the opinion of the treating physician-investigator that this is necessary to save the life of the patient. This decision will be up to the treating physician, but the study chair should be informed.

6.2 Definition of Dose-Limiting Toxicity

DLT Period. DLTs will be evaluated only in the Phase 1b – Safety Run-in Period. The period defined for evaluation of DLT is from the first day of pinometostat administration (day 1) to day 42 after induction, or if a re-induction was attempted, day 42 after re-induction.

Non Hematologic DLT will be determined based on non-hematologic Grade ≥ 3 toxicity related to the study drug alone or the study drug in combination with chemotherapy that occurs within first cycle of the combination. Severity of AEs will be graded according to National Cancer Institute Common Terminology Criteria for Adverse Events (CTCAE) v5. **With the following exceptions:** Grade 3 fatigue < 7 days; correctable electrolyte abnormalities within 72 hours; isolated, asymptomatic AST or ALT (<Grade 4) in the absence of significant bilirubin elevation (<Grade 3) that resolves within 7 days of drug hold; isolated, asymptomatic amylase elevation (<Grade 4) in the absence of lipase elevation (<Grade 3) that resolves within 7 days of drug hold. Pinometostat may be re-initiated in these patients at 60 mg/m² (no matter whether the patient was receiving 90 mg/m² or 60 mg/m²), and re-escalated (if patient was previously on 90 mg/m²; otherwise not applicable) if it does not recur; Grade 3 diarrhea that resolved to \leq Grade 1 or baseline in a week after receiving the maximal supportive therapy based on standard practice Grade 3 nausea and/ or vomiting (excluding need for TPN) that resolved to \leq Grade 1 or baseline in a week after the use of an optimal antiemetic regimen based on standard practice.

Hematologic DLT will be provisionally defined as an absolute neutrophil count (ANC) < 500/ μ L by day 42 (of first or second induction if applicable) in patients with < 5% blasts in the bone marrow, absence of myelodysplastic changes, and/or absence of evidence of disease by flow cytometry in the bone marrow. Neupogen in this setting may be administered. If persistent cytogenetic abnormalities or immunophenotypic evidence of leukemia is present, myelosuppression would be considered secondary to leukemia even if morphology shows < 5% blasts. Beyond the provisional assignment by day 42, patients who meet above hematologic DLT criteria and continue to have neutrophil < 500/ μ L shall have repeat bone marrow biopsy by day 56. During this additional 2 week period, patients who continue to meet the hematologic DLT criteria shall be DLTs; patients who have evidence of count recovery will not be DLTs.

For patients with > 5% blasts, myelodysplastic changes, or evidence of disease by flow cytometry/cytogenetics, failure to recover neutrophil or platelet count may not be considered DLT as this could be the result of persistent disease.

Also to be considered as DLT: 1) Failure to administer $\geq 75\%$ of planned doses (including in the denominator days needed for re-induction, if any) of the study drug due to therapy related or possibly related non-hematologic toxicities during the defined DLT period. 2) Other related Grade 2 or greater non-hematological toxicities that, in the opinion of the investigator, require a dose reduction or discontinuation of therapy with pinometostat.

All AEs and laboratory toxicities will be graded using the CTCAE version 5.

Management and dose modifications associated with the above adverse events are outlined in Section 6.

Dose escalation will proceed within each cohort according to the following scheme. Dose-limiting toxicity (DLT) is defined above.

Dose escalation will be performed in the usual 3+3 fashion. See Figure 2. Briefly, 3 patients will be enrolled on cohort 1. If zero of three patients experience dose-limiting toxicities (DLT), proceed to enroll cohort 2. If one of three patients experience DLT, enroll an additional three patients for a total of six patients on cohort 1. If still only one of six total patients experience DLT, proceed to enroll cohort 2. If 2 or more (of either three total or six total patients) experience DLT, accrual will be stopped and a safety review and consideration of further dose level reductions will be discussed between PI, CTEP, and stakeholders. Cohort 2 will be evaluated likewise, except that no further dose level increases will be made, and if toxicity is unacceptable in cohort 2, the dosing plan for cohort 1 will move forward into the expansion phase. Otherwise, the dosing plan for cohort 2 will move forward into phase II expansion.

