7. DOSING DELAYS/DOSE MODIFICATIONS

No intra-patient adjustment of chemotherapy doses is permitted. No intra-patient escalation of study drug is permitted, except as outlined below and with permission of principal investigator. Dose reduction of pinometostat should occur for grade 3 toxicities possibly related to this agent,

excluding hematologic toxicities and select other toxicities that can occur in the phase 2 expansion portion of the study. These select other toxicities for which a dose adjustment is not required include nausea, vomiting, or diarrhea that is manageable without parenteral or enteral feeding; electrolyte abnormalities that are correctable within 48 hours; and grade 3 infections which are expected in this population.

Daunorubicin and cytarabine are only rarely held during the seven-day intensive induction therapy for AML. Dose modifications to daunorubicin or cytarabine are not recommended for treatment-emergent adverse events, and should be discussed with the principal investigator. For patients with a total bilirubin between 1 and 1.5xULN, the daunorubicin dose may be decreased by 75% after discussion with the principal investigator.

| Event | Management/Next Dose for Pinometostat |
|---------------------|--|
| ≤ Grade 1 | Full dose |
| Grade 2 | Full dose |
| Grade 3 | Hold until recovery of < grade 3, then re-initiate with a one-third dose reduction. For example, if the dose was 90 mg/m ² /day, re-initiate at 60 mg/m ² /day. If the dose was 60 mg/m ² /day, re-initiate at 40 mg/m ² /day. If toxicity reoccurs, therapy should be discontinued. See exceptions in section 6, Dose Limiting Toxicities |
| Grade 4 | Discontinue therapy permanently. |

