9. STATISTICAL CONSIDERATIONS

9.1 Study Design/Endpoints

This study is a multi-site phase 1b/2 study designed to confirm a safe and tolerable dose of pinometostat and to gauge preliminary evidence of efficacy when given as lead-in prior to and contemporaneous with standard intensive induction therapy for newly diagnosed AML with MLL rearrangement. The study design involves a brief safety run-in phase exploring two dosing

schemes, followed by a phase II efficacy expansion. The phase II expansion will use the higher dose-level of the two schedules if tolerated (see definitions below), otherwise, the lower dose-level if tolerated. The phase 1b/safety run-in portion will have a primary endpoint of dose limiting toxicity, while the phase 2 portion will have a primary endpoint of complete remission / complete remission with incomplete count recovery attainment, and will gather additional laboratory correlative data.

The phase 1b safety run-in phase involves dividing patients into two cohorts (cohort 1 and cohort 2) after appropriate screening. The goal will be to identify a maximum tolerated dose for expansion. Dose escalation will occur in the standard cohorts-of-3/3+3 design, which is described below. Cohort 1 will comprise of 3-6 patients and will be treated with pinometostat 90 mg/m² continuous IV infusion (CIVI) on days 1-7, then decrease dose to 60 mg/m² CIVI for days 8-35, along with daunorubicin 60 mg/m² daily on days 8-10 and cytarabine 100 mg/m² CIVI on days 8-14. Cohort 2 will comprise of 3-6 patients and will be treated with pinometostat 90 mg/m² CIVI on days 1-35, along with daunorubicin 60 mg/m² daily on days 8-10 and cytarabine 100 mg/m² CIVI on days 8-14.

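### The pinometostat restart rules in sections 6.2 and 7 do not account for Cohort 1's planned step from 90 to 60 mg/m²/day on day 8

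*Combined protocol and SAP*

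**What the plan says.** All references are to the combined protocol and SAP.

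- **Cohort 1 schedule (6.1.1 and 9.1).** Pinometostat 90 mg/m² "continuous IV infusion (CIVI) on days 1-7, then decrease dose to 60" mg/m² for days 8-35, with 7+3 starting on day 8.
- **Cohort 2 schedule (same sections).** 90 mg/m² "CIVI on days 1-35, along with daunorubicin" and cytarabine, with no step.
- **Restart under 6.2.** Isolated transaminase or amylase elevations are exempt from the DLT definition if of a kind "that resolves within 7 days of drug hold". Pinometostat may then restart at 60 mg/m², "no matter whether the patient was receiving 90" or 60. If the event does not recur, the dose may be raised again: "and re-escalated (if patient was previously on 90" mg/m²). The clause names no target dose, study day or cohort.
- **Restart under section 7.** For a Grade 3 event: "Hold until recovery of < grade 3, then re-initiate with a one-third dose reduction". The worked examples are 90 to 60 and 60 to 40 mg/m²/day. The row refers the reader to the exceptions in section 6. The section also bars raising a patient's dose, except as it sets out and with the principal investigator's permission.

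**The concern.** Both restart rules read as if each patient had one constant assigned dose. That is true in Cohort 2 but not in Cohort 1, where every patient is on 90 during the lead-in and is due to be on 60 from day 8. An event in the lead-in can therefore meet a restart that falls after the planned step, and two things follow.

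(a) Under 6.2 the patient restarts at 60, which is the scheduled dose by then. The patient also satisfies the condition for re-escalation, having been on 90. Going back to 90 would put a Cohort 1 patient on Cohort 2's dose alongside or after 7+3.

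(b) Under section 7 a one-third cut from 90 is 60, which the patient was due to receive anyway.

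The 3+3 decision on Cohort 1 rests on three to six patients, so each is between 1/6 and 1/3 of the evidence. The escalation review needs to know which patients actually followed the schedule being judged. If Cohort 2 proves intolerable, Cohort 1's plan goes into the expansion, and the same question arises there.

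**Working it through.** **1. The plan's own figures.** Section 7's examples reproduce: 90 × 2/3 = 60 and 60 × 2/3 = 40.

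**2. Scheduled dose (mg/m²).**

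| | Days 1-7 | Days 8-35 | Total |
|---|---|---|---|
| Cohort 1 | 7 × 90 = 630 | 28 × 60 = 1,680 | 2,310 |
| Cohort 2 | 7 × 90 = 630 | 28 × 90 = 2,520 | 3,150 |

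**3. When the restart falls after the step.** Let the drug be held from event day d (1 to 7) for h whole days (1 to 7, the limit in the 6.2 exception), so restart day = d + h. For each d, exactly d values of h give a restart on day 8 or later: 1 + 2 + … + 7 = 28 of 49 combinations. This counts cases; it is not a probability.

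- In those 28, restart at 60 equals the scheduled 60, so the reduction after restart is 0.
- In the other 21, restart is on days 2-7 at 60 against a scheduled 90. That is a real reduction of 30 mg/m²/day for 1 to 6 days (30 to 180 mg/m²), ending at day 8. Re-escalation to 90 within days 1-7 stays on schedule.

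**4. Case (a): re-escalation under 6.2.** The documents give no re-escalation day and no target, so both are assumed here. With an event on day 7, a one-day hold, restart on day 8 at 60 and return to 90 on day 15:

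- Days 8-35: 7 × 60 + 21 × 90 = 420 + 1,890 = 2,310. (That this equals Cohort 1's planned 35-day total is coincidence.)
- Against Cohort 1's schedule: 2,310 − 1,680 = 630 more.
- Against Cohort 2's schedule: 2,310 / 2,520 = 92%.

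For the range, keep the day-7 event and let restart day r run from 8 to 14 and re-escalation come k = 0 to 7 days later. The days 8-35 dose is 60k + 90(36 − r − k) = 3,240 − 90r − 30k.

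- Highest (r = 8, k = 0): 2,520, the Cohort 2 amount.
- Lowest (r = 14, k = 7): 1,770, still above 1,680 despite six held days in that period.

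**5. Case (b): one-third cut under section 7.** With an event on day 7, a one-day hold and restart on day 8:

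- Base = dose at the event: 90 × 2/3 = 60. Days 8-35: 28 × 60 = 1,680, as scheduled. The 35-day total is 6 × 90 + 1,680 = 2,220 against 2,310; the 90 lost is the one held day.
- Base = dose scheduled on the restart day: 60 × 2/3 = 40. Days 8-35: 28 × 40 = 1,120, one-third below schedule.

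Section 7's examples favour the first base. The section does not say what happens when the schedule changes during the hold.

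**The case against.** The strongest reply is that the text already controls this. Re-escalation under 6.2 is optional, limited to exempt transaminase or amylase events, conditional on non-recurrence and, through section 7, subject to the principal investigator's permission. The study calendar (Table 11.1) gives the dose as assigned, and Cohort 1's assigned dose from day 8 is 60. On that view, 90 after day 8 is read into a silence. These limits stand and make the event uncommon. They do not settle the conflict: the only condition 6.2 attaches to prior dose is one that every Cohort 1 lead-in patient meets, and no criterion for the permission is stated.

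On case (b), the patient does restart a third below the dose at which the event occurred, and stops if it recurs. In phase 1b, a related non-exempt Grade 3 non-hematologic event is already a DLT, so it is not hidden from the 3+3 rule. Both points stand. It remains true that, apart from held days, nothing changes against the cohort's schedule.

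A reader might infer that a patient taken back to 90 falsely clears Cohort 1. The documents do not support that: tolerating more drug is not weaker evidence about the lower schedule, and a DLT after re-escalation would count against Cohort 1, which is conservative. Nor should such a patient be dropped from the tally. Section 9.1 makes anyone with at least one dose evaluable for DLT, and leaves it to the principal investigator to decide whether more patients are needed at that level.

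**Conclusion.** The conflict is real but narrow. It concerns Cohort 1 patients with an event at 90 in the lead-in who restart on day 8 or later. For them 6.2, read literally, permits a dose above the cohort's schedule, and section 7's rule, read by its own example, leaves the scheduled dose unreduced.

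In the illustration the excess is 630 mg/m² over days 8-35 (2,310 against 1,680). Over the assumed range the days 8-35 dose runs from 1,770 to 2,520. These figures assume a return to 90, whole-day holds of up to 7 days and re-escalation within 7 days of restart.

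Three broader readings are tempting and not supported:

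- That a lead-in event always ends in no reduction or in over-dosing. Restarts before day 8 give a real, if short, reduction.
- That both rules fix absolute doses. Only 6.2 does; section 7 is proportional.
- That all 31 efficacy patients would be affected if Cohort 1's plan is expanded. That is a ceiling: only patients with a qualifying lead-in event are concerned, the documents give no rate for these, and section 13.1 requires an approved amendment before phase 2 opens.

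Re-induction at 90 (6.1.3) is expressly provided for and is a separate matter.

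**What to change.** Reconcile 6.2 and section 7 with the Cohort 1 schedule in 6.1.1 and 9.1:

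1. State the restart dose and the re-escalation dose relative to one named reference, either the dose at the event or the cohort's scheduled dose for that study day, and use it in both sections.
2. State whether 6.2 allows a Cohort 1 patient to exceed the scheduled dose after day 7. The clinical team chooses the doses; none is proposed here.
3. Flag in the DLT listing any Cohort 1 patient who received more than the scheduled dose, so that the dose-escalation review can use the discretion it already has under 9.1. Do not exclude such a patient from the DLT count automatically.

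The cost is a few sentences in two sections and one flag in a listing. The sample size and the Simon design are unaffected.

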6.3 Monitoring

Monitoring of all safety and toxicity data is done by the Principal Investigator and the Corresponding Organization on a real-time basis as data are entered into Medidata Rave using the Web Reporting Module. All participating sites are expected to notify the Principal Investigator when a DLT has occurred.

6.4 General Concomitant Medication and Supportive Care Guidelines

Because there is a potential for interaction of pinometostat with other concomitantly administered drugs, the case report form must capture the concurrent use of all other drugs, over-the-counter medications, or alternative therapies. For example, the potential targets for drug interaction can involve, but are not limited to CYP450, glucuronidation, P-glycoprotein, protein binding, or reduced absorption from proton-pump inhibitors. Check the study agent Investigator's Brochure for potential sources of drug interactions. The study team should check a frequently-updated medical reference for a list of drugs to avoid or minimize use of. As the study treatment is given only in the inpatient setting, a Patient Drug Information Handout and Wallet Card will not be provided to patients.

Pinometostat is metabolized by CYP3A and to a minor extent by CYP2C19. It is a substrate of MATE2K and likely a weak substrate for OATP1B3, MATE1, and P-gp. It is a weak to moderate inhibitor of CYP3A and also an inhibitor of MATE1 and MATE2K. Use caution when administered with strong inhibitors and inducers of CYP2C19, OATP1B3, P-gp, MATE1, and MATE2K. Use caution with concomitant use of other CYP3A and MATE1 and MATE2-K substrates, especially those with a narrow therapeutic window.

6.5 Duration of Therapy

In the absence of treatment delays due to adverse event(s), treatment may continue for 35 days (note that this clock is reset in the event of reinduction and the treatment may continue for up to 28 days thence) or until one of the following criteria applies:

- Disease progression
- Intercurrent illness that prevents further administration of treatment
- Unacceptable adverse event(s)
- Patient decides to withdraw from the study
- General or specific changes in the patient's condition render the patient unacceptable for further treatment in the judgment of the investigator
- Clinical progression
- Patient non-compliance
- Pregnancy
 - All women of child bearing potential should be instructed to contact the investigator immediately if they suspect they might be pregnant (e.g., missed or late menstrual period) at any time during study participation.
 - The investigator must immediately notify CTEP in the event of a confirmed pregnancy in a patient participating in the study.
- Termination of the study by sponsor
- The drug manufacturer can no longer provide the study agent

The reason(s) for protocol therapy discontinuation, the reason(s) for study removal, and the corresponding dates must be documented in the Case Report Form (CRF).

6.6 Duration of Follow Up

Patients will be followed until the earliest of progressive disease, allogeneic stem-cell transplant, other investigational anti-leukemia therapy including cell therapy given while in remission, or lost to follow-up which will lead to removal from the study, or until death, whichever occurs first. Patients removed from study for unacceptable adverse event(s) will be followed until resolution or stabilization of the adverse event.

